## 1.0 TRIAL SUMMARY

Abbreviated Title	Pembrolizumab after hemithoracic radiation therapy for lung intact mesothelioma
Trial Phase	I
Clinical Indication	Curative intent
Trial Type	
Type of control	None
Route of administration	IV
Trial Blinding	None
Treatment Groups	Single arm
Number of trial subjects	24
Estimated enrollment period	12-16 months
Estimated duration of trial	18-24 months
Duration of Participation	18-24 months

## 2.0 TRIAL DESIGN

### 2.1 Trial Design

[figure not shown]
This trial is a single-arm study assessing the role of Pembrolizumab after induction chemotherapy +/- lung-sparing surgery for malignant pleural mesothelioma (MPM). Twelve patients will receive induction chemotherapy with a standard regimen (cisplatin/pemetrexed), followed by surgical resection if feasible with a lung-sparing approach (extrapleural pneumonectomy excluded), followed by hemithoracic radiation therapy with intensity modulated radiation therapy (IMRT) or proton beam therapy (PBT) to a total dose of 45 Gy in 25 fractions to the entire hemithorax, with an optional simultaneous integrated boost of 60 Gy in 25 fractions. Patients then will receive Pembrolizumab, 200 mg every 3 weeks until one of three timepoints (whatever comes first): 1) progression, 2) unacceptable toxicity, 3) 2 years.

In addition, we will enroll 12 additional patients with MPM who receive radiation for palliative reasons to a limited field (non-hemithoracic). This latter group of patients will be enrolled so that the abscopal/systemic effect can be evaluated in the context of very limited treatment options, to include patients that are not candidates for extensive radiation therapy.

[figure not shown]
These two independent cohorts of 12 patients will be accrued simultaneously but monitored separately, as outlined in the Statistical Methods section below.

## 2.2 Trial Diagram

### Cohort 1. Patients with Lung Intact to Receive Hemithoracic Radiation Therapy for Definitive Intent

### Cohort 2. Patients with Lung Intact to Receive Limited Field, Palliative Radiation Therapy

## 3.0 OBJECTIVE(S) & HYPOTHESIS(ES)

### 3.1 Primary Objective(s) & Hypothesis(es)

(1) **Objective:** To determine the safety and tolerability of pembrolizumab administered after radiation therapy in patients with MPM who have not undergone extrapleural pneumonectomy. Two cohorts will be included, one receiving extensive hemithoracic radiation and the other receiving more limited, palliative treatment. These cohorts will be accrued simultaneously but monitored separately for toxicity.

**Hypothesis:** Pembrolizumab will be well tolerated when given after radiation therapy for MPM.

## 3.2 Secondary Objective(s) & Hypothesis(es)

(1) **Objective:** To assess progression-free and overall survival (PFS and OS, respectively) in patients receiving Pembrolizumab after radiation therapy for MPM.

**Hypothesis:** Adding Pembrolizumab to radiation therapy for MPM will improve PFS and OS compared to historical controls.

## 3.3 Exploratory Objective

(1) **Objective:** To evaluate biomarkers of interest, including cytokines, measurements of T-cell activation, and serum exosome microRNAs with the delivery of Pembrolizumab after radiation therapy for MPM.

# 4.0 BACKGROUND & RATIONALE

## 4.1 Background

Malignant pleural mesothelioma (MPM) occurs in approximately 2000-3000 new individuals each year in the United States.[1] MPM remains a difficult disease to treat with median overall survival rates remaining between 9–17 months, regardless of stage.[2-4] In patients that present with locoregionally confined disease (e.g. non-metastatic), the standard of care for definitive intent has historically involved induction chemotherapy followed by an extrapleural pneumonectomy (EPP=removal of the ipsilateral lung, pleura, diaphragm, and pericardium) and consideration of postoperative radiation therapy. However, many patients cannot tolerate an EPP, and as a result this resection is not a viable option for a large percentage of patients. In addition, several recent clinical studies have concluded that an EPP does not provide a survival advantage over lung sparing approaches, including a pleurectomy/decortication (e.g. “stripping” of the pleura without removing the lungs) or no surgery.

[figure not shown]
Specifically, The Mesothelioma and Radical Surgery trial (MARs)[5, 6] which compared 50 randomized MPM patients to EPP (n=24) versus “no EPP” (n=26) reported that receipt of EPP led to a worse survival (hazard ratio (HR) 1.90, 95% CI 0.92 – 3.93, p=0.082). In this study, only 16 of the 24 patients in the EPP arm actually received the EPP and 19% (n=3) had post-operative deaths. After accounting for prognostic factors (stage, histology, gender, age), the HR for EPP was reported as 2.75 (p=0.016). The median overall survival was 14.4 months for patients in the EPP arm compared to 19.5 months for the patients in the “no EPP” arm. This trial, although limited in numbers of patients, suggested that at worst, EPP can harm patients and at best, there was no clinical benefit for MPM patients. In addition, Lang-Lazdunski et al.[7] conducted a nonrandomized study of consecutive MPM patients and compared 25 who received neoadjuvant chemotherapy followed by EPP and radiation to 54 patients with P/D, hyperthermic lavage, adjuvant radiation and chemotherapy. The study reported that the P/D arm was superior to the EPP arm for compliance, toxicity and survival. Patients in the P/D arm had 100% compliance to complete trimodality treatment versus 68%

in the EPP arm. The P/D arm also had a higher median overall survival of 23 months versus 12.8 months.[7]

Studies such as these have suggested that patients are optimally treated with lung sparing approaches. However, radiation therapy when the ipsilateral lung is intact, with or without surgery, presents unique issues. First, the presence of functional lung tissue on the same side as the target volume exposes the patient to the risk of radiation pneumonitis in this lung. Second, presuming that the ipsilateral lung is functional, patients can theoretically experience significant functional decline due to the difficulty in sparing this structure. Finally, if much of the ipsilateral lung is nonfunctional after RT, a “shunting” effect can occur whereby patients continue to perfuse to the ipsilateral lung, yet air exchange does not occur. For these reasons, hemithoracic radiation treatment with two functional lungs can paradoxically be more challenging than with only one lung intact.

[figure not shown]
However, a limited number of institutions, including ours, have utilized advanced techniques to treat patients that do not undergo EPP with hemithoracic radiation therapy in the definitive setting. The first of these approaches is IMRT, and **Figure 1** depicts a representative IMRT plan in this setting. We have recently published our results of 22 patients who underwent P/D followed by adjuvant IMRT to the involved hemithorax. Patients were treated to 45 Gy in 25 fractions with 9 patients receiving a simultaneous boost to 60 Gy to high risk areas. Twenty patients received chemotherapy (15=induction, 2=adjuvant, 3=both). Median follow up was 14.7 months after surgery (range 4.1-37.1 months). The therapy was well tolerated. No grade 4-5 pulmonary toxicity was noted. One case of grade 4 thrombocytopenia was observed. Progressive decreases in pulmonary function were noted after surgery and IMRT. Median baseline % predicted FVC, FEV1, and DLCO were 90%, 84%, and 87%. The change in % predicted FVC, FEV1 and DLCO was -18%, -11% and -17% after surgery and -25% (p=0.02), -18% (p=0.01), and -27% (p=0.01) after IMRT. Rates of overall survival and progression free survival were 73% and 60% at 1 year, respectively, and 52% and 32% at 2 years, respectively. Outcomes for IMRT after P/D were compared to 22 matched patients who underwent IMRT after EPP. The patients who underwent P/D had less grade 4-5 toxicity (0/22 vs 3/22, p=0.23) and a trend towards improved median overall survival (28.4 vs 14.2 months, p=0.14), median disease free survival (15.4 vs 10.2 months, p=0.18), and median time to distant metastasis (not reached vs 11.8 months, p=0.15). [8] Thus, these results suggested that hemithoracic radiation after P/D provides comparable toxicity and efficacy as after EPP.

**Figure 1. IMRT treatment plan with the lung intact.**

Indeed, other reports have also been consistent with these findings. Between 2005 and 2010, 36 patients from Memorial Sloan-Kettering Cancer Center (MSKCC) with malignant pleural mesothelioma who were unable to undergo pneumonectomy underwent induction chemotherapy (89% of patients) and then P/D with adjuvant IMRT (56%) or IMRT with biopsy only (44%). All patients were treated to the pleural surface of the involved hemithorax to a median dose of 46.8 Gy. Seven (20%) patients developed high grade pneumonitis (including 1 death). For patients who underwent PL/D prior to IMRT, the 1- and 2-year survival rate was 75% and 53%, and the median survival was 26 months. For patients who did not undergo surgical resection, the 1- and 2-year survival rate and median survival trended lower at 69% and 28%, and 17 months respectively.[9] These investigators also recently examined patterns of failure when treating the external pleural hemithorax in 67 patients to a similar volume as Figure 2. The rate of in-field local failure was 64%, with 1- and 2-year total failure rates of 56% and 74%, respectively. Interestingly, the authors also found that failure within the fissures was 16%, and only 1 patient had an incisional failure despite the practice of not routinely boosting the incisional sites [10]. Based on these two trials, we have recently completed a prospective study in conjunction with MSKCC examining the efficacy of patients treated with induction chemotherapy, then P/D or no surgery, followed by hemithoracic radiation therapy with IMRT. Thirty nine patients enrolled, and in an interim report 21 patients completed IMRT. Only one patient experienced Grade 3 pneumonitis, a rate below that which is often reported for locally advanced non-small cell lung cancer (NSCLC).[11]

A second radiation technique that can be used to further increase normal tissue sparing is PBT, specifically intensity modulated proton therapy (IMPT). Proton particles provide a dose distribution advantage by delivering less dose proximal and distal to the target region, with a sharper dose falloff (known as the “Bragg Peak”). IMPT has been studied in multiple malignancies, including NSCLC [12-14]. In addition, we have recently reported our early experience with IMPT for lung-intact malignant pleural mesothelioma, in which we found lower doses to multiple structures, including the contralateral lung, heart, and esophagus. As a result, we continue to treat select patients with this technique [15]. **Figure 2** shows an IMPT plan in a patient with the ipsilateral lung intact.

**Figure 1. Proton beam therapy (IMPT) treatment plan with the lung intact.**

In this study, we assess the role of conformal radiation techniques as part of a lung-sparing regimen with immunotherapy in patients with malignant pleural mesothelioma. Specifically, we are combining radiation therapy with Pembrolizumab, and we ***hypothesize that through the utilization of inhibitors of the PD1/PDL1 axis after radiation therapy in MPM, we will improve rates of both local and distant disease control by taking advantage of the complementary biologic effects of the two modalities.***

Note that in addition to enrolling 12 patients with MPM who will receive induction chemotherapy and hemithoracic radiation therapy, we will also enroll 12 additional patients who will receive palliative radiation therapy to a limited field (non-hemithoracic), to assess the safety/efficacy of this approach. In particular, this cohort of patients will allow us to assess the abscopal/systemic effect that has been observed in patients receiving radiation therapy and immunotherapy outside of the radiation field. We will also be able to assess outcomes in the context of delivering less aggressive radiation fields. Indeed, it may be the case that when immunotherapeutic agents are delivered, more limited fields can be used to provide analogous rates of disease control as in a hemithoracic field, but with more limited toxicity. We will be able to accrue to these two arms concurrently, which will also increase accrual rates and with one trial break for toxicity assessment halfway through each arm.

There is evidence for the immune checkpoint process playing an active role in MPM. Both the T-cell inflamed phenotype and PD-L1 expression have been observed in this malignancy, particularly in non-epithelioid tumors. In addition, PD-L1 expression is associated with a poorer prognosis [16]. And recently, results from the KEYNOTE-028 trial were presented at the American Association for Cancer Research annual meeting. Investigators enrolled 25 patients with MPM and PD-L1 positive disease who were then treated with Pembrolizumab for 24 months or until progression/intolerable toxicity. They observed a 28% objective response rate and a 76% disease control rate that was better than the historical response for second-line chemotherapy. As a result, these findings were encouraging for

further evaluation of this agent in MPM. The current study would be the first of its kind to combine Pembrolizumab with radiation therapy.[17]

#### **4.1.1 Pharmaceutical and Therapeutic Background**

The importance of intact immune surveillance in controlling outgrowth of neoplastic transformation has been known for decades. Accumulating evidence shows a correlation between tumor-infiltrating lymphocytes (TILs) in cancer tissue and favorable prognosis in various malignancies. In particular, the presence of CD8+ T-cells and the ratio of CD8+ effector T-cells / FoxP3+ regulatory T-cells seems to correlate with improved prognosis and long-term survival in many solid tumors.

The PD-1 receptor-ligand interaction is a major pathway hijacked by tumors to suppress immune control. The normal function of PD-1, expressed on the cell surface of activated T-cells under healthy conditions, is to down-modulate unwanted or excessive immune responses, including autoimmune reactions. PD-1 (encoded by the gene *Pdcd1*) is an Ig superfamily member related to CD28 and CTLA-4 which has been shown to negatively regulate antigen receptor signaling upon engagement of its ligands (PD-L1 and/or PD-L2). The structure of murine PD-1 has been resolved. PD-1 and family members are type I transmembrane glycoproteins containing an Ig Variable-type (V-type) domain responsible for ligand binding and a cytoplasmic tail which is responsible for the binding of signaling molecules. The cytoplasmic tail of PD-1 contains 2 tyrosine-based signaling motifs, an immunoreceptor tyrosine-based inhibition motif (ITIM) and an immunoreceptor tyrosine-based switch motif (ITSM). Following T-cell stimulation, PD-1 recruits the tyrosine phosphatases SHP-1 and SHP-2 to the ITSM motif within its cytoplasmic tail, leading to the dephosphorylation of effector molecules such as CD3 $\zeta$ , PKC $\theta$  and ZAP70 which are involved in the CD3 T-cell signaling cascade. The mechanism by which PD-1 down modulates T-cell responses is similar to, but distinct from that of CTLA-4 as both molecules regulate an overlapping set of signaling proteins. PD-1 was shown to be expressed on activated lymphocytes including peripheral CD4+ and CD8+ T-cells, B-cells, Tregs and Natural Killer cells. Expression has also been shown during thymic development on CD4-CD8- (double negative) T-cells as well as subsets of macrophages and dendritic cells. The ligands for PD-1 (PD-L1 and PD-L2) are constitutively expressed or can be induced in a variety of cell types, including non-hematopoietic tissues as well as in various tumors. Both ligands are type I transmembrane receptors containing both IgV- and IgC-like domains in the extracellular region and contain short cytoplasmic regions with no known signaling motifs. Binding of either PD-1 ligand to PD-1 inhibits T-cell activation triggered through the T-cell receptor. PD-L1 is expressed at low levels on various non-hematopoietic tissues, most notably on vascular endothelium, whereas PD-L2 protein is only detectably expressed on antigen-presenting cells found in lymphoid tissue or chronic inflammatory environments. PD-L2 is thought to control immune T-cell activation in lymphoid organs, whereas PD-L1 serves to dampen unwarranted T-cell function in peripheral tissues. Although healthy organs express little (if any) PD-L1, a variety of cancers were demonstrated to express abundant levels of this T-cell inhibitor. PD-1 has been suggested to regulate tumor-specific T-cell expansion in subjects with melanoma (MEL).

This suggests that the PD-1/PD-L1 pathway plays a critical role in tumor immune evasion and should be considered as an attractive target for therapeutic intervention.

Pembrolizumab is a potent and highly selective humanized monoclonal antibody (mAb) of the IgG4/kappa isotype designed to directly block the interaction between PD-1 and its ligands, PD-L1 and PD-L2. Keytruda™ (pembrolizumab) has recently been approved in the United States for the treatment of patients with unresectable or metastatic melanoma and disease progression following ipilimumab and, if BRAF V600 mutation positive, a BRAF inhibitor.

#### **4.1.2 Preclinical and Clinical Trial Data**

Refer to the Investigator's Brochure for Preclinical and Clinical data.

### **4.2 Rationale**

#### **4.2.1 Rationale for the Trial and Selected Subject Population**

Please see section 4.1 for a detailed description of the rationale for this trial. We will enroll patients with malignant pleural mesothelioma who do not undergo an EPP, the rationale being that these patients often have a worse prognosis, with limited treatment options. Therefore, we are aiming to benefit these patients using our highly conformal radiation techniques in combination with Pembrolizumab.

#### **4.2.2 Rationale for Dose Selection/Regimen/Modification**

An open-label Phase I trial (Protocol 001) is being conducted to evaluate the safety and clinical activity of single agent Pembrolizumab. The dose escalation portion of this trial evaluated three dose levels, 1 mg/kg, 3 mg/kg, and 10 mg/kg, administered every 2 weeks (Q2W) in subjects with advanced solid tumors. All three dose levels were well tolerated and no dose-limiting toxicities were observed. This first in human study of Pembrolizumab showed evidence of target engagement and objective evidence of tumor size reduction at all dose levels (1 mg/kg, 3 mg/kg and 10 mg/kg Q2W). No MTD has been identified to date. 10.0 mg/kg Q2W, the highest dose tested in PN001, will be the dose and schedule utilized in Cohorts A, B, C and D of this protocol to test for initial tumor activity. Recent data from other clinical studies within the Pembrolizumab program has shown that a lower dose of Pembrolizumab and a less frequent schedule may be sufficient for target engagement and clinical activity.

A population pharmacokinetic analysis has been performed using serum concentration time data from 476 patients. Pembrolizumab has been found to have a wide therapeutic range based on the melanoma indication. The differences in exposure for a 200 mg fixed dose regimen relative to a 2 mg/kg Q3W body weight based regimen are anticipated to remain well within the established exposure margins of 0.5 – 5.0 for Pembrolizumab in the melanoma indication. The exposure margins are based on the notion of similar efficacy and safety in melanoma at 10 mg/kg Q3W vs. the proposed dose regimen of 2 mg/kg Q3W (i.e.

5-fold higher dose and exposure). In addition, exposure was similar between the NSCLC and melanoma indications. Therefore, there are no anticipated changes in exposure between different indication settings.

The rationale for further exploration of 2 mg/kg and comparable doses of pembrolizumab in solid tumors is based on: 1) similar efficacy and safety of pembrolizumab when dosed at either 2 mg/kg or 10 mg/kg Q3W in melanoma patients, 2) the flat exposure-response relationships of pembrolizumab for both efficacy and safety in the dose ranges of 2 mg/kg Q3W to 10 mg/kg Q3W, 3) the lack of effect of tumor burden or indication on distribution behavior of pembrolizumab and 4) the assumption that the dynamics of pembrolizumab target engagement will not vary meaningfully with tumor type.

The choice of the 200 mg Q3W as an appropriate dose for the switch to fixed dosing is based on simulations showing that the fixed dose of 200 mg every 3 weeks will provide exposures that 1) are optimally consistent with those obtained with the 2 mg/kg dose every 3 weeks, 2) will maintain individual patient exposures in the exposure range established in melanoma as associated with maximal efficacy response and 3) will maintain individual patients exposure in the exposure range established in melanoma that are well tolerated and safe.

A fixed dose regimen will simplify the dosing regimen to be more convenient for physicians and to reduce potential for dosing errors. A fixed dosing scheme will also reduce complexity in the logistical chain at treatment facilities and reduce wastage.

#### **4.2.3 Rationale for Endpoints**

Given the lack of experience combining radiation therapy for MPM and immunotherapy, the primary endpoint will be high-grade toxicity, defined specifically in Table 3 below. Specifically, the Off-Study Criteria defined in Table 3 are the “Unacceptable” high-grade toxicities in the trial. That is, patients that meet these criteria will be considered as having met the study endpoint and will be taken off study. Patients will be monitored for 4 months after the start of RT. Since RT is approximately 1 month in duration, this monitoring period will include 3 months after the end of RT.

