## 4.4 Trial Treatments

The treatment to be used in this trial is outlined below in Table 2

Table 2 Trial Treatment

Drug	Dose/Potency	Dose Frequency	Route of Administration	Regimen/Treatment Period	Use
Pembrolizumab	200 mg X mg/kg	Q3W	IV infusion	Day 1 of each 3 week cycle	Experimental

Note: Patients must initiate treatment with Pembrolizumab within 1 month of the last day of radiation therapy.

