#### **4.4.4.3 Treatment Planning and Prescription Dose**

##### **Cohort 1 – Hemithoracic Radiation Therapy**

Patients will be prescribed a prescription dose of 45 Gy in 25 fractions to the PTV, and 2.4 Gy x 25 fractions to the GTV (if applicable) using a simultaneous integrated boost. Either IMRT or IMPT will be utilized, using techniques described in prior publications from our institutions [15, 18].

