##### **Cohort 2 – Non-Hemithoracic Radiation Therapy**

Patients will be treated to one of the following prescribed doses: a) 3 Gy x 10 fractions = 30 Gy, b) 4 Gy x 5 fractions = 20 Gy, c) 5 Gy x 5 fractions = 25 Gy, or d) 45-52.5 Gy in 15 fractions. Patients will be treated using either IMRT or 3D conformal therapy.

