### **7.2 Statistical Analysis Plan**

We will enroll a total of 24 patients, twelve patients to each cohort consisting of distinct radiation and immunotherapy treatment plans. For each study cohort, treatment-related toxicity is defined in Table 3 above (in the column “Discontinue Treatment/Off-Study Criteria”. Therefore, any patient meeting this criteria will be deemed to have experienced an “unacceptable” toxicity for the purposes of the trial. For each study condition, we plan to enroll 12 patients in cohorts of size 6. All patients will be monitored for at least 4 months from the beginning of RT, before declaring the treatment acceptable for enrolling the next cohort of 6 patients.

Continuous monitoring using the method of Thall [20] will be employed for each study cohort of 12 patients in cohorts of size 6 where each patient is monitored for at least 4 months from the start of RT. We will stop the trial if we have reason to believe that the treatment-related toxicity rate is more than 30%. Using the following probability rule

$$\Pr(\text{rate of treatment-related toxicity 4 months from the start of RT} > 30\% \mid \text{data}) > 0.80.$$

If we determine there is more than a 80% chance that the treatment-related toxicity rate is more than 30%, we will stop the trial. We will assume a beta(0.6, 1.4) distribution for treatment-related toxicity as this prior provides a mean of 30% and a standard deviation of 26.5%. Thus the trial will be stopped if

$$[\# \text{ of patients with treatment-related toxicity 4 months from day 1 of the start of RT} / \# \text{ of patients evaluated}]$$

$$\geq 3/6, 6/12$$

Therefore, we will stop either study cohort if we observe 3 or more treatment-related toxicities in the first 6 patients, or if we observe 6 treatment related toxicities at any time while evaluating all 12 patients. We will suspend accrual while evaluating the first 6 patients to ensure none of

the stopping boundaries have been reached prior to enrolling the final 6 patients of each study cohort. The operating characteristics from this decision rule are shown in Table X and are based on 1000 simulations for each scenario.

Table X. Operating characteristics for toxicity monitoring rule

Treatment-related Toxicity 4 months after start of RX	Probability of Stopping Early	Sample Size Avg
0.10	0.017	11.9
0.20	0.099	11.4
0.30	0.254	10.5
0.40	0.462	9.2
0.50	0.650	8.1

- Operating Characteristics acquired using the Stata command stopbound

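### The 4-month toxicity window runs from the start of RT and guarantees no minimum time on pembrolizumab, the drug whose safety is the primary objective

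*Combined protocol and SAP*

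**What the plan says.** All references are to the combined protocol and SAP.

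- **Objective (section 3.1):** "To determine the safety and tolerability of pembrolizumab administered after radiation therapy in patients with MPM", in two cohorts monitored separately.
- **Window (section 4.2.3):** "Patients will be monitored for 4 months after the start of RT". The reason given is one RT duration for both cohorts: "Since RT is approximately 1 month in duration, this monitoring period will include 3 months after the end of RT".
- **Stopping rule (section 7.2):** "All patients will be monitored for at least 4 months from the beginning of RT" before the next six patients are enrolled. Both the probability statement and the boundary count toxicity at 4 months from RT start. Each cohort has the same 30% limit, Beta(0.6, 1.4) prior, 0.80 cut-off and boundary of 3/6 and 6/12.
- **RT (section 4.4.4.3):** for Cohort 1, "Patients will be prescribed a prescription dose of 45 Gy in 25 fractions to the PTV". Cohort 2 has a choice of schedules with 5, 10 or 15 fractions, among them "5 Gy x 5 fractions = 25 Gy".
- **Start of drug (note to Table 2, section 4.4):** "Patients must initiate treatment with Pembrolizumab within 1 month of the last day of radiation therapy". No minimum gap is given. Doses follow every 3 weeks (section 4.4.2).
- **Evaluability (section 6.1.4.1):** a patient with Grade 3 or higher toxicity during RT is non-evaluable. No section requires a minimum number of pembrolizumab doses.

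**The concern.** The clock of the primary endpoint starts at RT, but the objective concerns the drug that follows RT. The RT part of the window contributes little to the count, since a severe event during RT removes the patient from the evaluable set. What remains depends on two things that the window ignores: the number of fractions and the delay to the first dose. Two evaluable patients, even within one cohort, can therefore contribute quite different times on pembrolizumab to the same 3/6 and 6/12 counts.

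At stake is how a decision not to stop is read. A cohort of late starters could pass the first look with about two months of drug exposure per patient. The text on radiation pneumonitis after Table 3 uses the results to say whether the combination should be taken further in neither setting, only the limited-field one, or both.

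**Working it through.** **1. The plan's own figures.** The posterior probability that the rate exceeds 30%, with x events in n patients, comes from Beta(0.6 + x, 1.4 + n − x). It is 0.523 at 2/6, 0.800 at 3/6, 0.772 at 5/12 and 0.905 at 6/12. The boundary of 3/6 and 6/12 reproduces.

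The exact chance of 3 or more events in 6 at true rates of 0.10, 0.20, 0.30, 0.40 and 0.50 is 0.016, 0.099, 0.256, 0.456 and 0.656. Table X gives 0.017, 0.099, 0.254, 0.462 and 0.650 from 1000 simulations. The table is sound. The question is what exposure the counts represent.

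**2. Time on drug within the window.** Assumptions: 5 fractions per week starting on a Monday, 4 months = 122 days, first dose 1 to 30 days after the last RT day.

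- First dose day = last RT day + gap
- Days on drug = 122 − first dose day
- Scheduled doses = whole part of (days on drug / 21) + 1

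| RT | Last RT day | First dose day | Days on drug | Scheduled doses |
|---|---|---|---|---|
| Cohort 1, 25 fractions | 33 | 34 to 63 | 88 to 59 | 5 to 3 |
| Cohort 2, 15 fractions | 19 | 20 to 49 | 102 to 73 | 5 to 4 |
| Cohort 2, 10 fractions | 12 | 13 to 42 | 109 to 80 | 6 to 4 |
| Cohort 2, 5 fractions | 5 | 6 to 35 | 116 to 87 | 6 to 5 |

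Cohort 1 spans 59 to 88 days and Cohort 2 spans 73 to 116, so they overlap. At equal delay the difference is the difference in RT length: 33 − 19 = 14 to 33 − 5 = 28 days. Taking 4 months as 120 days lowers each figure by 2 days and leaves the cohort dose ranges at 3 to 5 and 4 to 6. At 112 days the overall range is still 3 to 6 doses.

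**3. What this could do to the rule (illustration only).** Suppose a constant hazard after the first dose gives 30% at 12 weeks: p(d) = 1 − 0.7^(d/84). The documents give no such hazard. With X₁ and X₂ the event counts in the first and second six patients, the two-look stopping probability is P(X₁ ≥ 3) + Σ P(X₁ = a) · P(X₂ ≥ 6 − a), summed over a = 0, 1, 2.

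| Gap after RT | Cohort | Days | p(d) | P(stop) |
|---|---|---|---|---|
| 1 day | 1 | 88 | 0.31 | 0.31 |
| 1 day | 2 | 102 to 116 | 0.35 to 0.39 | 0.40 to 0.49 |
| 30 days | 1 | 59 | 0.22 | 0.135 |
| 30 days | 2 | 73 to 87 | 0.27 to 0.31 | 0.21 to 0.30 |

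At equal delay the cohorts differ by about 0.08 to 0.18. Within Cohort 1 alone, start delay moves the figure from 0.31 to 0.135, a change of about 0.17.

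**4. Effect of the proposed window.** The shortest exposure becomes 84 days. Doses on days 0, 21, 42, 63 and 84 make 5, the last on the closing day. Exposure becomes 84 to 88 days in Cohort 1 and 84 to 116 in Cohort 2. The largest extension is 63 + 84 − 122 = 25 days in Cohort 1 and 49 + 84 − 122 = 11 days in Cohort 2.

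**The case against.** Anchoring at RT start is defensible for a combined regimen. Section 7.1 describes the study as assessing the toxicity of two radiation plans. Table 3 counts Grade 3 or greater radiation-related toxicity as off-study, and the pneumonitis text applies the same 3/6 and 6/12 limits to radiation pneumonitis. Such events run on a clock from RT. This stands, and it is why the 4 months from RT start should be kept as one limb of the window.

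No comparison between cohorts is planned. Each is monitored separately against its own boundary, so a shared 30% limit is not in itself a fault. This also stands. A reader might infer that the shorter exposure makes the hemithoracic regimen look safer than it is. The documents do not support that: the illustration uses a drug-only hazard, while the endpoint mixes drug and radiation toxicity, and radiation toxicity may well differ with field size.

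A reader might also set 0.135 (59 days) against 0.49 (116 days) as the cohort effect. That pairs the latest starters in one cohort with the earliest in the other. The same one-month allowance applies to both, so the fair contrast holds the delay equal.

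Nor is the 3-month statement in section 4.2.3 unmet for Cohort 2, which has about 103 to 117 days after RT. The stated RT duration is loose for that cohort, but the follow-up described is there.

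Finally, monitoring is for at least 4 months, adverse events are recorded to 30 days and serious ones to 90 days after treatment, and toxicities are tabulated for each cohort. Later events will be seen. They do not enter the formal rule, which counts at 4 months from RT start.

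**Conclusion.** The point holds as a minor one. The window that drives the stopping rule sets no floor on pembrolizumab exposure, and with a late but permitted start it can hold as few as 59 days and 3 scheduled doses. The gap arises within each cohort through start delay, and between cohorts through RT length.

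The day counts rest on 5 fractions per week, 30 days for a month's delay and 122 days for 4 months. The dose counts are scheduled doses, before holds and the 3-day dosing window. The stopping probabilities rest on an assumed constant hazard and show only that differences of this size can matter to the rule. No direction of bias between cohorts is shown, and the boundary and Table X are not in question.

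**What to change.** In sections 4.2.3 and 7.2, define the evaluation window in both cohorts as ending at the later of 4 months after RT start and 12 weeks after the first pembrolizumab dose. Use the same definition in the probability statement and the boundary. Report the number of doses received within the window, by cohort. In section 4.2.3, give the RT duration separately for Cohort 2.

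The change keeps the RT-anchored 4 months and leaves the treatment schedule untouched. It sets a common floor and does not equalise exposure for early starters, which is why the dose report is needed.

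The cost is a wording change and some time. Accrual is suspended at the first look, so each look may come up to about 25 days later in Cohort 1 and about 11 days later in Cohort 2. Nothing moves for patients who start soon after RT.
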